## 10.7.2. Age-Specific Kidney Function Calculation Recommendations

2021 CKD-EPI	Scr (mg/dL)	Scys (mg/L)	Recommended eGFR Equation
Scr Only			
Female	if ≤0.7	N/A	$eGFR = 143 \times (Scr/0.7)^{-0.241} \times (0.9938)^{Age}$
Female	if >0.7	N/A	$eGFR = 143 \times (Scr/0.7)^{-1.200} \times (0.9938)^{Age}$
Male	if ≤0.9	N/A	$eGFR = 142 \times (Scr/0.9)^{-0.302} \times (0.9938)^{Age}$
Male	if >0.9	N/A	$eGFR = 142 \times (Scr/0.9)^{-1.200} \times (0.9938)^{Age}$
2021	Scr	Scys	Recommended eGFR Equation
CKD-EPI	(mg/dL)	(mg/L)	
Scr-Scys			
Combined			
Female	if ≤0.7	if ≤0.8	$eGFR = 130 \times (Scr/0.7)^{-0.219} \times (Scys/0.8)^{-0.323} \times (0.9961)^{Age}$
Female	if ≤0.7	if >0.8	$eGFR = 130 \times (Scr/0.7)^{-0.219} \times (Scys/0.8)^{-0.778} \times (0.9961)^{Age}$
Female	if >0.7	if ≤0.8	$eGFR = 130 \times (Scr/0.7)^{-0.544} \times (Scys/0.8)^{-0.323} \times (0.9961)^{Age}$
Female	if >0.7	if >0.8	$eGFR = 130 \times (Scr/0.7)^{-0.544} \times (Scys/0.8)^{-0.778} \times (0.9961)^{Age}$
Male	if ≤0.9	if ≤0.8	$eGFR = 135 \times (Scr/0.9)^{-0.144} \times (Scys/0.8)^{-0.323} \times (0.9961)^{Age}$
Male	if ≤0.9	if >0.8	$eGFR = 135 \times (Scr/0.9)^{-0.144} \times (Scys/0.8)^{-0.778} \times (0.9961)^{Age}$
Male	if >0.9	if ≤0.8	$eGFR = 135 \times (Scr/0.9)^{-0.544} \times (Scys/0.8)^{-0.323} \times (0.9961)^{Age}$
Male	if >0.9	if >0.8	$eGFR = 135 \times (Scr/0.9)^{-0.544} \times (Scys/0.8)^{-0.778} \times (0.9961)^{Age}$

### 10.7.2.1. Adults (18 Years and Above)-2021 CKD-EPI Equations

Inker LA et al. N Engl J Med. 2021;385:1737-49.18

## 10.7.3. Adverse Event Grading for Kidney Safety Laboratory Abnormalities

AE grading for decline in kidney function (ie, eGFR or eCrCl) will be according to CTCAE criteria.

#### 10.8. Appendix 8: ECG Findings of Potential Clinical Concern

## ECG Findings That May Qualify as AEs Marked sinus bradycardia (rate <40 bpm) lasting minutes. New PR interval prolongation >280 ms. New prolongation of QTcF to >480 ms (absolute) or by $\geq$ 60 ms from baseline. New-onset atrial flutter or fibrillation, with controlled ventricular response rate: ie, rate <120 bpm. New-onset type I second-degree (Wenckebach) AV block of >30 seconds' duration. Frequent PVCs, triplets, or short intervals (<30 seconds) of consecutive ventricular complexes. ECG Findings That May Qualify as SAEs QTcF prolongation >500 ms. New ST-T changes suggestive of myocardial ischemia. New-onset LBBB (QRS complex >120 ms). New-onset right bundle branch block (QRS complex >120 ms). Symptomatic bradycardia. Asystole: In awake, symptom-free participants in sinus rhythm, with documented periods of asystole $\geq$ 3.0 seconds or any escape rate <40 bpm, or with an escape rhythm that is below the AV node; In awake, symptom-free participants with atrial fibrillation and bradycardia with 1 or more pauses of at least 5 seconds or longer; Atrial flutter or fibrillation, with rapid ventricular response rate: rapid = rate >120 bpm.

• Sustained supraventricular tachycardia (rate >120 bpm) ("sustained" = short duration with relevant symptoms or lasting >1 minute).

- Ventricular rhythms >30 seconds' duration, including idioventricular rhythm (HR <40 bpm), accelerated idioventricular rhythm (HR 40 bpm to <100 bpm), and monomorphic/polymorphic ventricular tachycardia (HR >100 bpm [such as torsades de pointes]).
  - Type II second-degree (Mobitz II) AV block.
  - Complete (third-degree) heart block.

## ECG Findings That Qualify as SAEs

- Change in pattern suggestive of new myocardial infarction.
- Sustained ventricular tachyarrhythmias (>30 seconds' duration).
- Second- or third-degree AV block requiring pacemaker placement.
- Asystolic pauses requiring pacemaker placement.
- Atrial flutter or fibrillation with rapid ventricular response requiring cardioversion.
- Ventricular fibrillation/flutter.
- At the discretion of the investigator, any arrhythmia classified as an adverse experience.

The enumerated list of major events of potential clinical concern are recommended as "alerts" or notifications from the core ECG laboratory to the investigator and Pfizer study team, and not to be considered as all-inclusive of what to be reported as AEs/SAEs.

## 10.9. Appendix 9: Comfort and Wearability Questionnaire

Par	ticipant ID					
1. D	ate of Assessment (dd-MMM-yyyy)					
2. D	evice Placement		WRIST JOINT			
Nan	ne of the person completing this fo	orm				
		Questio	ons	-		
		Strongly Disagree	Disagree	Neutral	Agree	Strongly Agree
3.a	The device is comfortable to wear	$\bigcirc$	$\bigcirc$	$\bigcirc$	$\bigcirc$	$\bigcirc$
3.b	The device is easy to put on	$\bigcirc$	$\bigcirc$	$\bigcirc$	$\bigcirc$	$\bigcirc$
3.c	The device is easy to take off	$\bigcirc$	$\bigcirc$	$\bigcirc$	$\bigcirc$	$\bigcirc$
3.d	The device is easy to wear	$\bigcirc$	$\bigcirc$	$\bigcirc$	$\bigcirc$	$\bigcirc$
3.e	The device changes the way I move (e.g., walking)	$\bigcirc$	$\bigcirc$	$\bigcirc$	$\bigcirc$	$\bigcirc$
3.f	The device changes the way I behave	$\bigcirc$	$\bigcirc$	$\bigcirc$	$\bigcirc$	$\bigcirc$
3.g	I am willing to wear the device for 4 to 7 days	$\bigcirc$	$\bigcirc$	$\bigcirc$	$\bigcirc$	$\bigcirc$
3.h	I am willing to wear the device for more than 7 days	$\bigcirc$	$\bigcirc$	$\bigcirc$	$\bigcirc$	$\bigcirc$
3.i	If the device could follow change in my activity levels during treatment, I would wear it	$\bigcirc$	$\bigcirc$	$\bigcirc$	$\bigcirc$	$\bigcirc$
3.j	If the device could follow change in my activity levels, I would want my doctor to have access to my results	$\bigcirc$	$\bigcirc$	$\bigcirc$	$\bigcirc$	$\bigcirc$

Participant ID						
1. D	1. Date of Assessment (dd-MMM-yyyy)					
2. D	evice Placement		LUMBAR REGION			
Nan	ne of the person completing this fo	orm				
		Questio	ons			
		Strongly Disagree	Disagree	Neutral	Agree	Strongly Agree
3.a	The device is comfortable to wear	$\bigcirc$	$\bigcirc$	$\bigcirc$	$\bigcirc$	$\bigcirc$
3.b	The device is easy to put on	$\bigcirc$	$\bigcirc$	$\bigcirc$	$\bigcirc$	$\bigcirc$
3.c	The device is easy to take off	$\bigcirc$	$\bigcirc$	$\bigcirc$	$\bigcirc$	$\bigcirc$
3.d	The device is easy to wear	$\bigcirc$	$\bigcirc$	$\bigcirc$	$\bigcirc$	$\bigcirc$
3.e	The device changes the way I move (e.g., walking)	$\bigcirc$	$\bigcirc$	$\bigcirc$	$\bigcirc$	$\bigcirc$
3.f	The device changes the way I behave	$\bigcirc$	$\bigcirc$	$\bigcirc$	$\bigcirc$	$\bigcirc$
3.g	I am willing to wear the device for 4 to 7 days	$\bigcirc$	$\bigcirc$	$\bigcirc$	$\bigcirc$	$\bigcirc$
3.h	I am willing to wear the device for more than 7 days	$\bigcirc$	$\bigcirc$	$\bigcirc$	$\bigcirc$	$\bigcirc$
3.i	If the device could follow change in my activity levels during treatment, I would wear it	$\bigcirc$	$\bigcirc$	$\bigcirc$	$\bigcirc$	$\bigcirc$
3.j	If the device could follow change in my activity levels, I would want my doctor to have access to my results	$\bigcirc$	$\bigcirc$	$\bigcirc$	$\bigcirc$	$\bigcirc$

## 10.10. Appendix 10: ECOG Performance Status

GRADE	ECOG PERFORMANCE STATUS
0	Fully active, able to carry on all pre-disease performance without restriction
1	Restricted in physically strenuous activity but ambulatory and able to carry out work of a light or sedentary nature, eg, light house work, office work
2	Ambulatory and capable of all selfcare but unable to carry out any work activities; up and about more than 50% of waking hours
3	Capable of only limited selfcare; confined to bed or chair more than 50% of waking hours
4	Completely disabled; cannot carry on any selfcare; totally confined to bed or chair
5	Dead

## 10.11. Appendix 11: RECIST 1.1 Tumor Assessment Criteria RECIST (Response Evaluation Criteria In Solid Tumors) version 1.1 Guidelines

Adapted from Eisenhauer E.A., et al.

\*Since MRIs are not included in this study, the RECIST criteria only applies to CT scans.

## CATEGORIZING LESIONS AT BASELINE

### Measurable Lesions

Lesions that can be accurately measured in at least one dimension.

- Lesions with longest diameter twice the slice thickness and at least 10 mm or greater when assessed by CT or MRI\* (slice thickness 5-8 mm).
- Lesions with longest diameter at least 20 mm when assessed by Chest X-ray.
- Superficial lesions with longest diameter 10 mm or greater when assessed by caliper.
- Malignant lymph nodes with the short axis 15 mm or greater when assessed by CT.

## NOTE: The shortest axis is used as the diameter for malignant lymph nodes, longest axis for all other measurable lesions.

### Non-measurable disease

Non-measurable disease includes lesions too small to be considered measurable (including nodes with short axis between 10 and 14.9 mm) and truly non-measurable disease such as pleural or pericardial effusions, ascites, inflammatory breast disease, leptomeningeal disease, lymphangitic involvement of skin or lung, clinical lesions that cannot be accurately measured with calipers, abdominal masses identified by physical exam that are not measurable by reproducible imaging techniques.

- Bone disease: Bone disease is non-measurable with the exception of soft tissue components that can be evaluated by CT or MRI\* and meet the definition of measurability at baseline.
- Previous local treatment: A previously irradiated lesion (or lesion subjected to other local treatment) is non-measurable unless it has progressed since completion of treatment.

#### Normal sites

- Cystic lesions: Simple cysts should not be considered as malignant lesions and should not be recorded either as target or non-target disease. Cystic lesions thought to represent cystic metastases can be measurable lesions, if they meet the specific definition above. If non-cystic lesions are also present, these are preferred as target lesions.
- Normal nodes: Nodes with short axis <10 mm are considered normal and should not be recorded or followed either as measurable or non-measurable disease.

## **RECORDING TUMOR ASSESSMENTS**

All sites of disease must be assessed at baseline. Baseline assessments should be done as close as possible prior to study start. For an adequate baseline assessment, all required scans must be done within 28 days prior to treatment and all disease must be documented appropriately. If baseline assessment is inadequate, subsequent statuses generally should be indeterminate.

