### Table 1. Schedule of Activities for Part A Double-Blind

Visit Identifier	Screening				I	Part A: Do	ouble-Bl	ind a		F/U Part A	ED Part A
Abbreviations used in this table may be found in											
Week #			4	5 b,c	8 d	9 c,e (PK	10 c,f	11 с,е (РК	12	16	
						substudy only)		substudy only)			
Day -relative to start of study intervention (Day 1)	-28 to -7	1	29	36	57	64	71	78	85	113	
Visit Window (Days)			±3	-3/+7	±3	±2	±7/±3 f	±2	±2	+7	
Blood sample for immunogenicity (ADA and Nab) i		Х	X		Х				Х	Х	Х
Blood sample for albumin & pre-albumin		Х							Х		Х
Study Intervention and Other Treatments											
Registration within IRT	X										
Randomization		Х									
Study intervention administration		Х	Х		Х				Xa		
Prior/concomitant treatment(s)	X	Х	Х		Х				Х	Х	Х
Assessments											
Efficacy											
Weight j	X	Х	X	Х	X		X		Х	Х	Х
PRO-CRCSD k	X	$\rightarrow$	$\rightarrow$	$\rightarrow$	$\rightarrow$	$\rightarrow$	$\rightarrow$	$\rightarrow$	Х		Х
PRO-PROMIS (fatigue 7A & physical function 8c) 		Х	X		Х				Х		Х
PRO-FAACT 		Х	X		Х				Х		Х
PRO-PGI-S (appetite, fatigue and physical function) 		Х	Х		Х				Х		Х
PRO-PGI-C (appetite, fatigue, and physical function) 			Х		Х				Х		Х
PRO-PGI-S (physical activity and walking) m	Х				Х		X		Х		Х
PRO-PGI-C (physical activity and walking) m					Х		X		Х		Х
Digital Measures-physical activity and gait n	X→				X→		$X \rightarrow$	$\rightarrow$	Х		Х
Comfort and Wearability Questionnaire for Digital									Х		Х
Measures (At clinic)											
Qualitative Exit Interview o									Х		Х
Safety											
CT scan p	X								Х		Х
Serious and nonserious AE monitoring	X	$\rightarrow$	$\rightarrow$	$\rightarrow$	$\rightarrow$	$\rightarrow$	$\rightarrow$	$\rightarrow$	$\rightarrow$	$\rightarrow$	$\rightarrow$
Retained Research Samples (not applicable for											
China)											
Retained research sample for genetics (Prep D1.5) q,r		X									

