#### Table 1. Schedule of Activities for Part A Double-Blind

Visit Identifier	Screening			Part A: Double-Blind a F/U							ED Part A
Abbreviations used in this table may be found in	_										
Appendix 13											
Week #			4	5 b,c	8 d	9 с,е (РК	10 c,f	11 c,e (PK	12	16	
						substudy only)		substudy only)			
Day -relative to start of study intervention (Day 1)		1	29	36	57	64	71	78	85	113	
	-28 to -7										
Visit Window (Days)			±3	-3/+7	±3	±2	±7/±3 f	±2	±2	+7	

1. Data will be captured using the electronic PRO device at the clinic and should be completed by the participant at the beginning of the visit before any medical procedures or interactions with the medical staff takes place (as much as practically possible). See Section 8.2.2.

m. Data will be captured using the electronic PRO device either at home or at the clinic. Measured immediately at the end of the 7-day consecutive monitoring period for Screening (at home), Week 8 (approximately Day 63 at home), Week 10 (approximately Day 77 at home), and Week 12 (approximately Day 85 at the clinic). The Week 12 assessment is to be collected prior to the first dose of study intervention for participants proceeding with Part B OLT. See Section 8.2.2.

 Measured during Screening, Week 8 (period of Week 8-9) and Week 12 (period of Week 10-12) for a minimum 7 days, using the electronic device at home. See Section 8.2.3.

- o. Phone Interview will be conducted by the vendor within the 10 business days following the Week 12 visit, or at ED, if feasible. See Section 8.2.2.
- p. All CT scans will need to include chest, abdomen, and pelvis to be acceptable for this study. If a SOC CT scan was performed within 3 weeks prior to the Screening visit, then a CT scan at screening is not needed. If a SOC CT scan is being performed at the Week 12 visit, between Weeks 10-12 or within 7 days after the Week 12 visit as part of SOC, then an additional CT scan is not needed. Similarly, if SOC CT scan is performed 2 weeks prior or 7 days after the ED visit, then an additional CT scan is not needed. The RECIST 1.1 categorization (Appendix 11) is to be entered in the CRF after each scan. See Section 8.3.7.

q. If not collected on the designated collection day, collect at the next available time point when biospecimens are being collected in conjunction with a participant visit.

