#### 8.1.1. Screening Visit

The Screening visit will occur no more than 28 days and no less than 7 days, prior to Randomization. The 7-day minimum duration between Screening and Randomization visits will ensure that the GDF-15 results and the 7-day collection of PRO and physical activity data are available to inform the investigator's assessment of eligibility.

At the Screening visit only, the evaluation of the Fearon Criteria eligibility criteria is to be assessed using the participant's body weight from their medical record. If the participant's body weight is unavailable from medical record, the participant's weight is to be captured utilizing question 1 of the PG-SGA questionnaire.

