#### 8.3.7. Imaging Assessment-CT Scan

#### 8.3.7.1. Imaging Safety Assessment

CT scans will be acquired during the study to monitor the tumor burden. All CT scans will need to include chest, abdomen, and pelvis to be acceptable for this study.

If SOC CT scan with chest, abdomen, and pelvis was performed within 3 weeks prior to the Screening the visit, then a CT scan at Screening is not needed. If a SOC CT scan is being performed at the Week 12 visit, between Weeks 10-12 or within 7 days after the Week 12

visit as part of SOC, then an additional CT scan is not needed. Similarly, if SOC CT scan is performed 2 weeks prior or 7 days after the ED visit, then an additional CT scan is not needed.

Monitoring of the tumor burden will be performed by the site following standard RECIST 1.1 criteria (outlined in Appendix 11). The RECIST 1.1 categorization is to be entered in the CRF after each scan.

All follow up testing and final diagnosis will be left to the discretion of the medical professionals at the site or those with an existing physician participant relationship. The PI will be responsible for reporting any AEs identified from incidental findings as described in the AE reporting section.

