3.4.8.2. PGI-S

The PGI-S consists of 5 questions that ask the study participants to evaluate the severity of their appetite loss, fatigue, physical function, limitations of physical activity and walking over the past 7 days, on a 5-point verbal response scale that ranges from "None" to "Very severe".

The PGI-S is recommended by FDA for use as an anchor measure to generate an appropriate threshold that represents meaningful within individual change in the target patient population.

The change from baseline in PGI-S will be calculated for all post-baseline timepoints.

3.4.9. Tumor status according to RECIST 1.1 guidelines using CT scan at Week 12

CT scans will be acquired during the study to monitor the tumor burden. Monitoring of the tumor burden will be performed by the site following standard RECIST 1.1 criteria (outlined in Appendix 11 of the protocol).

3.4.10. Change from baseline in LSMI derived from CT scans at Week 12; Percent change from baseline in skeletal muscle and adipose tissue measures derived from CT scans at Week 12

CT scans will also be submitted to a central imaging vendor for the measurement of body composition (skeletal muscle area and adipose tissue areas at the 3rd lumbar vertebral level).

The endpoints are:

- LSMI (cm²/m²): LSMI = skeletal muscle area (cm²) / height (m)²
- Skeletal muscle area (cm²)
- Subcutaneous adipose area (cm²)
- Visceral adipose area (cm²)
- Intramuscular adipose area (cm²)
- Skeletal muscle radio-attenuation (Hounsfield Units, HU)
- Subcutaneous adipose radio-attenuation (Hounsfield Units, HU)
- Visceral adipose radio-attenuation (Hounsfield Units, HU)

Intramuscular adipose radio-attenuation (Hounsfield Units, HU)

Baseline is defined as the last measurement prior to, or on, study day 8. Change from baseline for LSMI will be calculated for all post baseline timepoints.

Percent change from baseline for the remaining skeletal muscle and adipose tissue measures will be calculated for all post baseline timepoints.

Percent change from baseline in radio-attenuation measurements at post baseline timepoints will be excluded for a participant if the IV contrast used at that timepoint is different to that used at baseline.

Additional exploratory body composition measurements may be performed but may not be reported in the CSR.

3.4.11. Change from baseline albumin and pre-albumin levels at Week 12

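### The Schedule of Activities can accept a baseline CT up to 49 days before first dose, while Appendix 11 sets a 28-day limit for the same exploratory tumour-status endpoint

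*Protocol*

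**What the plan says.** **Which scans are accepted.** Footnote p to Table 1 of the Protocol's Schedule of Activities states: "If a SOC CT scan was performed within 3 weeks prior to the Screening visit, then a CT scan at screening is not needed". Section 8.3.7.1 repeats the rule, and the risk table in Section 2.3.1 cites it as a way to limit radiation exposure.

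**When Screening happens.** Protocol Section 8.1.1: "The Screening visit will occur no more than 28 days and no less than 7 days, prior to Randomization". Table 1 places both randomization and the first administration of study intervention on Day 1.

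**What counts as an adequate tumour baseline.** Protocol Appendix 11, under Recording Tumor Assessments, requires that "all required scans must be done within 28 days prior to treatment". It then adds: "If baseline assessment is inadequate, subsequent statuses generally should be indeterminate".

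**How the result is used.** Sites assign the RECIST 1.1 category from Appendix 11 and enter it in the CRF (Section 8.3.7.1). SAP Section 6.4.9 tabulates tumour response by treatment in the Appendix 11 categories, and SAP Section 7.2.1 repeats this at the interim.

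**Body composition.** SAP Section 3.4.10, which covers LSMI, skeletal muscle and adipose measures, has its own rule: "Baseline is defined as the last measurement prior to, or on, study day 8". The general efficacy rule in SAP Section 3 stops at study day 1.

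**The concern.** The protocol gives two time limits for one scan. A site that follows the Schedule of Activities need not repeat a standard-of-care CT that Appendix 11 would call too old for an adequate baseline. At Week 12, one site may read the Appendix 11 sentence strictly and record an indeterminate status. Another may compare with the accepted scan and record stable disease or progression. Both would be following the protocol. The tumour-status table would then depend partly on how each site resolved the conflict, and the number of indeterminate results could not be interpreted cleanly.

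The body-composition rule raises a different and smaller issue. Taken literally, when a participant has one scan before dosing and another between Day 1 and Day 8, the post-dose scan becomes the baseline. LSMI is one of the few tertiary endpoints that SAP Section 5.1 tests against placebo, and baseline LSMI also defines sarcopenia status in SAP Section 3.5.

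**Working it through.** **Inputs**
- Longest Screening-to-Day 1 interval: 28 days; shortest: 7 days (Protocol Section 8.1.1; Table 1).
- Oldest standard-of-care CT accepted before Screening: 3 weeks = 21 days (Table 1 footnote p; Section 8.3.7.1).
- Limit for an adequate RECIST baseline: 28 days before treatment (Appendix 11).
- Anchor: randomization and first dose both on Day 1 (Table 1).

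**1. Greatest accepted scan age at first dose**
Longest screening lead + oldest accepted scan = 28 + 21 = 49 days.
Excess over Appendix 11 = 49 − 28 = 21 days.

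**2. When the two rules agree**
Under the 28-day limit, the oldest admissible scan before Screening is 28 minus the screening lead:

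| Screening lead (days) | Oldest admissible scan before Screening (days) |
|---|---|
| 7 | 21 |
| 14 | 14 |
| 21 | 7 |
| 28 | 0 |

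The full 3-week allowance fits only when Screening is exactly 7 days before dosing. A CT taken at the Screening visit itself always fits, so the conflict concerns substituted standard-of-care scans only.

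**3. How much of the permitted window conflicts**
There are 22 whole-day leads (7 to 28) and 22 whole-day scan ages (0 to 21), so 22 × 22 = 484 combinations. For a lead of s days, s − 7 of the scan ages give a total above 28. Summing 0 + 1 + … + 21 gives 231, and 231 / 484 = 48%. This counts permitted combinations; it does not forecast how many participants are affected.

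**4. The body-composition baseline**
Study day 8 is 8 − 1 = 7 days after the Day 1 dose. Table 1 schedules CT at Screening and at Week 12 or early discontinuation, with none on Days 1 to 8. A post-dose scan can therefore displace a pre-dose one only if an unscheduled scan falls in that week.

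The extremes of the baseline-to-Week 12 interval are:
- Shortest: Day 8 to Day 71 (Week 10, the earliest substituted scan) = 71 − 8 = 63 days.
- Longest: 49 days before Day 1, plus 84 days from Day 1 to Day 85, plus the 2-day visit window, plus the 7-day scan allowance = 49 + 84 + 2 + 7 = 142 days.

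Each figure combines the most extreme value of every window.

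**The case against.** The strongest reply has four parts.

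- **The footnote only waives a scan.** It spares radiation and does not declare the older scan adequate for RECIST; only Appendix 11 addresses adequacy. This is a fair reading, but it leaves the gap open: the schedule still admits scans that the criteria call inadequate, and no passage says what to record.
- **Appendix 11 is qualified.** A reader might infer that every participant with an older scan must be indeterminate. The text does not support that, because it says only what should generally happen. The discretion stands, but with no study-wide rule it is what allows sites to diverge.
- **The endpoint is minor.** Tumour status is tertiary/exploratory and summarised descriptively. This stands and limits the weight of the point.
- **The Day 8 rule is separate.** A reader might infer that it also breaches Appendix 11. It does not: it governs body composition only, while tumour status in SAP Section 3.4.9 falls under the general Day 1 rule.

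A reader might also infer from the 63-to-142-day range that the LSMI comparison is biased. The documents do not show that. Scans taken before dosing cannot reflect a treatment effect, and randomization should balance their timing on average, so the likelier cost is added noise. SAP version 3 also clarified the baseline wording after blinded data review. A rerun of the LSMI ANCOVA limited to scans within 28 days would borrow a limit written for tumour response; no passage requires it.

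**Conclusion.** The contradiction is real and neither document resolves it. An accepted baseline CT can be up to 49 days old at first dose, against a 28-day limit in the criteria that sites must apply, so participants whose scan is 29 to 49 days old can be coded inconsistently. This assumes, as Table 1 shows, that randomization and first dose fall on the same day. How many participants are affected cannot be derived from the documents.

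The consequence is confined to an exploratory table at the interim and final analyses. It would be too strong to say that the plan invalidates its tumour data or touches the body-weight analysis: the primary endpoint and the sample size do not use these scans.

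The Day 8 baseline is a separate and minor defect of wording, relevant only in the uncommon case where a participant has scans both before dosing and in the week after it.

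**What to change.** 1. **Protocol.** Reconcile Table 1 footnote p, Section 2.3.1 and Section 8.3.7.1 with Appendix 11 so that one window governs the baseline tumour scan. Which window to adopt is for the sponsor to decide.
2. **SAP Sections 3.4.9 and 6.4.9.** State one rule for deriving RECIST status when the accepted baseline scan is 29 to 49 days before treatment, and apply it to all sites and to the interim summary.
3. **SAP Section 3.4.10.** State that the last pre-dose scan is the body-composition baseline, and that a scan after dosing through Day 8 is used only when there is no pre-dose scan.

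An LSMI ANCOVA restricted by baseline scan age is optional.

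The cost is wording in a few places and one derivation rule in programming. No new scans, extra participants or changes to the primary analysis are needed.
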